#### 8.3.1. Time Period and Frequency for Collecting AE and SAE Information

All AEs and SAEs will be collected from the signing of the ICF until the follow-up visit at the time points specified in the SoA (Section 1.3).

All SAEs will be recorded and reported to Alexion or the designee immediately and under no circumstance should this exceed 24 hours, as indicated in Section 10.3. The Investigator will submit any updated SAE data to Alexion within 24 hours of it being available.

Investigators are not obligated to actively seek AEs or SAE data after conclusion of the study participation. However, if the Investigator learns of any SAE, including a death, at any time after a participant has been discharged from the study, and he/she considers the event to be reasonably related to the study drug or study participation, the Investigator must promptly notify Alexion.

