12.1. Adverse Events / Adverse Drug Reactions

AEs for all participants in the Safety Set will be included in the AE summaries.

Adverse events will be summarized by system organ class (SOC) and preferred term (PT) for each treatment and overall, based on the MedDRA dictionary version 23.1.

If the relationship to study drug is missing for TEAEs, then the relationship will be counted as related to study product for the summary tables. Missing severity for TEAEs will be counted as Grade 3.

Pretreatment AEs are defined as AEs that were reported or worsened after signing the ICF up to the start of study drug dosing. Treatment-emergent AEs are defined as AEs that were reported or worsened on or after the start of study drug dosing through the safety follow-up visit.

If the start date of an AE is partially or completely missing, the date will be compared as far as possible with the date of the start of administration of study drug. The AE will be assumed to be treatment-emergent if it cannot be definitively shown that the AE did not occur or increase in severity during the treatment period (worst case approach). The following general rules will be used:

- If the start day is missing but the start month and year are complete, an AE will not be considered as being treatment-emergent only if the start month/year is before the month/year of the first study drug administration.
- If the start day and month are missing but the start year is complete, an AE will not be considered as being treatment-emergent only if the start year is before the year of the first study drug administration.
- If the start date is completely missing, an AE will be considered treatment-emergent unless the stop date is before the first study drug administration.

Duration will be calculated for AEs that resolve as the difference between the resolution date and onset date plus 1 and expressed in days. Should an AE have a short duration (*i.e.* < 24 hours), the duration will be calculated as the difference between the resolution time and the onset time.

Adverse events of special interest are defined as any IRR equal to or higher than Grade 3; or any IRR that may jeopardize the participant and requires immediate intervention to prevent it from leading to severe outcomes. Potential cases of any delayed hypersensitivity reactions, equal to or higher than Grade 2.

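### SAP 12.1: the two partial-start-date rules ignore a known stop date, so an AE that ended before the first dose can be counted as treatment-emergent

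*SAP*

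**What the plan says.** SAP 12.1 opens its missing-date text with a worst-case approach: "The AE will be assumed to be treatment-emergent if it cannot be definitively shown that the AE did not occur or increase in severity" while on treatment. Three general rules follow.

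- **Rule 1, start day missing:** "an AE will not be considered as being treatment-emergent only if the start month/year is before the month/year of the first study drug administration".
- **Rule 2, start day and month missing:** "an AE will not be considered as being treatment-emergent only if the start year is before the year of the first study drug administration".
- **Rule 3, start date completely missing:** "an AE will be considered treatment-emergent unless the stop date is before the first study drug administration".

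The same section defines the two classes by their timing relative to dosing. The earlier class is set out thus: "Pretreatment AEs are defined as AEs that were reported or worsened after signing the ICF up to the start of study drug dosing". The later class, whose window closes at follow-up, is worded to match: "Treatment-emergent AEs are defined as AEs that were reported or worsened on or after the start of study drug dosing".

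Protocol 9.4.1 gives the same definitions and no date rules. No other part of either document applies a stop date to an AE with a partly known start date.

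**The concern.** In rules 1 and 2 the words *only if* make an earlier start month or year the sole ground for calling an AE not treatment-emergent. A recorded stop date before dosing cannot be used, although rule 3 accepts the same fact as decisive. A participant who remembers the month in which a symptom began can be classified less accurately than one who remembers nothing about its onset.

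The situation can arise. Under Protocol 8.3.1, "All AEs and SAEs will be collected from the signing of the ICF", and screening lasts up to 60 days, so pre-dose AEs enter the database. SAP 12.1 puts only TEAEs in the summary tables, and TEAE incidence is part of the primary endpoint. Two other defaults in SAP 12.1 can add to the effect: a TEAE with missing relationship is counted as related, and one with missing severity as Grade 3. An event that resolved before any drug was given could therefore appear as a related or Grade 3 TEAE.

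**Working it through.** The plan has no figure of its own to reproduce here. The check applies the three rules as written to AEs that ended before the first dose.

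**One case, two classes.** Assume a first dose on 15 March and an AE that stopped on 10 March of the same year.

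| Start date recorded | Rule | Class |
|---|---|---|
| Day unknown, March | 1 | treatment-emergent |
| Day and month unknown, same year | 2 | treatment-emergent |
| Nothing known | 3 | not treatment-emergent |

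**All start/stop pairs in the screening window.** An AE that starts k days before dosing (k = 1 to 60) can stop on any of k days and still end before the dose. The total number of pairs is 60 × 61 / 2 = 1830.

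- Rule 1 misclassifies a pair when the start falls in the dosing month. For a dose on day m of the month, with m no later than 31, that is (m − 1) × m / 2 pairs.
- Rule 2 misclassifies a pair when the start falls in the dosing year.
- Rule 3 misclassifies none.

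The documents give no dosing dates, so these are assumed (2021):

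| First dose | Rule 1 | Rule 2 | Rule 3 |
|---|---|---|---|
| 15 January | 14 × 15 / 2 = 105 (5.7%) | 105 (5.7%) | 0 |
| 1 March | 0 | 1830 − 60 = 1770 (96.7%) | 0 |
| 2 March | 1 (0.1%) | 1830 (100%) | 0 |
| 15 March or 15 July | 105 (5.7%) | 1830 (100%) | 0 |
| 31 March | 30 × 31 / 2 = 465 (25.4%) | 1830 (100%) | 0 |

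On 1 March the 60 pairs excluded by rule 2 are those starting on 31 December. With a stop-date test added to rules 1 and 2, every count becomes 0. These percentages describe how far the rules reach over possible date pairs. They are not expected error rates, because they treat all pairs as equally likely and say nothing about how often a start date is incomplete.

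**Size in the tables.** SAP 7.1 sets one active column per cohort and a single placebo column for all cohorts.

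- Full active column, n = 6: 1/6 = 16.7 percentage points.
- Pooled placebo: 2 in each of Cohorts 1, 3, 4 and 5 gives 8 if those cohorts filled as planned. SAP 4.1 reports 2 participants in Cohort 2 without giving their allocation, so the pool is 8 to 10. One participant is 1/10 = 10 to 1/8 = 12.5 points.
- The 16.7-point figure does not apply to Cohort 2, which has too few participants for percentages to be informative.

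These are ceilings. SAP 12.1 counts a participant once per SOC and once per PT, so an incidence row moves only if that participant has no genuine TEAE in it. The event count in the row rises by one in any case.

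**The case against.** The strongest reply is that the rules err on the safe side. The section declares a worst-case approach, the rules over-count rather than hide events, safety analysis is descriptive, and non-treatment-emergent AEs are listed separately. The rules are also described as general, under an instruction to compare dates as far as possible, so a sensible programmer might use the stop date anyway. The direction of the error is conceded. But the worst case is meant for what cannot be shown, and these events can be shown to have ended. *Only if* also reads against using the stop date, so two programmers could derive different flags for the primary safety tables.

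It can also be said that the definitions speak of AEs being reported, so a resolved event first mentioned after dosing might count as treatment-emergent. Rule 3 does not work that way: it lets the timing of the event decide.

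Four stronger readings are tempting, and the documents do not support them.

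- **That the rules breach the SAP's own principle.** The principle says what to assume when timing cannot be shown. It does not say that every AE shown to be pre-dose must be excluded. The inconsistency is with rule 3 and with the two definitions.
- **That one placebo participant shifts incidence by 50 points.** That needs a placebo column of two. The SAP's general layout pools placebo.
- **That 17 points is the expected effect.** It holds only in a full active column and only where the participant has no other TEAE in the row. Protocol 2.3.3 reports headache in 100% of participants at multiple 20 mg/kg IV doses, so many active participants may already count in the overall row.
- **That such AEs will occur.** An error needs a partial start date, a known stop date before dosing, and a known start month or year equal to that of dosing. The documents do not say how often these coincide. In healthy participants with AEs monitored continuously from consent and admission on Day -1, the number is probably small.

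**Conclusion.** The point holds as a minor drafting error with a definite effect. As written, rules 1 and 2 can place an AE that demonstrably ended before the first dose among the TEAEs, while rule 3 would exclude the same AE with less information. This conflicts with rule 3 and with the section's own class definitions, and it feeds the primary safety tables. It inflates TEAE counts and does not conceal events.

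The ceiling per misclassified participant is about 17 percentage points in a 6-participant active column and about 10 to 12.5 points in pooled placebo. These figures assume that Cohorts 1, 3, 4 and 5 filled as planned and that the participant has no other TEAE in the row. The actual effect cannot be quantified from the documents and may be nil.

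**What to change.** Place one sentence ahead of the three rules in SAP 12.1: *An AE whose stop date is known to be before the first study drug administration is not treatment-emergent, whatever part of the start date is missing.* Apply this check first, then the start-date rules as they stand.

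This extends the test already in rule 3. It cannot remove an AE that may have continued into treatment, because an AE with a missing stop date, or one not known to precede dosing, still falls to the worst-case rules. The cost is one sentence in the SAP and one line of derivation code, with no new data.

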12.2. Laboratory Evaluations

Safety laboratory samples for chemistry, hematology, urinalysis and coagulation will be collected at various different timepoints for different cohorts.

Refer to Section 1.3 of the Protocol for the schedule of activities indicating when the respective samples are taken for each cohort.

The following parameters will be included:

Clinical chemistry: BUN, chloride, potassium, bicarbonate, sodium, glucose, AST, ALT, alkaline phosphatase, gamma glutamyltransferase, HbA1C (Screening only), urea, total and direct bilirubin, total protein, albumin, cholesterol (total), LDL, HDL, triglycerides, creatinine, creatine phosphokinase.

Hematology: Platelet count, RBC count, hemoglobin, hematocrit, mean corpuscular volume, mean corpuscular hemoglobin, % reticulocytes, neutrophils, lymphocytes, monocytes, eosinophils, basophils.

Urinalysis: Specific gravity, pH, glucose, protein, blood, ketones, bilirubin, urobilinogen, nitrite, leukocyte esterase. Microscopic examination (if any leucocytes, more than a trace protein, nitrites, and blood [if not menstruating] are abnormal).

Coagulation: International normalized ratio, partial thromboplastin time, prothrombin time.

Serology: HIV-1 and HIV-2 antibodies, HBsAg, anti-HBC IgG + IgM (if IgG positive), and anti-HCV with confirmation by HCV RNA.

Serum hCG pregnancy test (as needed for women of childbearing potential), FSH (postmenopausal females only)

Alcohol breath and **urine drug screen:** Amphetamines, barbiturates, benzodiazepines, cocaine, opiates, phencyclidine, methamphetamine, 3,4-methylenedioxy-methamphetamine, methadone, and tetrahydrocannabinol [cannabinoids]) at minimum.

IRR: In the event of an IRR, it is recommended to collect a blood sample for assessment of tryptase, histamine, C-reactive protein, complement C3, complement C5a, complement C5, Interleukin 1 Beta, Interleukin 2, Interleukin 4, Interleukin 5, Interleukin 6, Interleukin 8, Interferon Gamma, Interleukin 10, Interleukin 12 and Tumor Necrosis Factor as soon as the IRR is observed (prior to administering any IRR medication), and 2 hours, 24 hours and 7 days (prior to the next dose of study drug) after onset of the IRR.

Signs of infection: If a participant shows signs of infection, the following investigations should be included:

- Blood cultures (taken prior to start of antibiotics)
- Routine profile

Laboratory parameter values will be graded according to the National Cancer Institute Common Terminology Criteria for Adverse Events (CTCAE).

All summaries will be based on results in SI (standard international system of units) units and will be

output in the order listed above.

Toxicity grading following the NCI CTCAE grades version 5.0 will also be derived for laboratory variables where applicable (see list below). Note, where gradings require investigator/clinical input, this will not be considered and only the numeric criteria will be used for the assignments. If this results in the criteria for more than one grade being met, the highest (worst) CTCAE grade will be assigned. For creatinine only, the criteria based on the upper limit of normal (ULN) will be used (changes compared to the baseline value will not be used), eg, CTCAE defines Grade 1 as > ULN - 1.5 x ULN or > 1 - 1.5 x baseline. Only the ULN – 1.5 x ULN criterion will be used (and not the baseline criterion).

The following parameters are CTCAE gradable:

- Clincal Chemistry: Alanine aminotransferase albumin, alkaline phosphatase, aspartate aminotransferase, total bilirubin, creatinine, gamma-glutamyl transferase, glucose (only do the grading the hypoglycemia, no grading for hyperglycemia), creatine kinase.
- **Hematology**: Absolute neutrophil count (neutrophil), total leukocytes (Leukocytes), hemoglobin (only do the grading for anemia, no grading for hemoglobin increased), platelet count, lymphocyte.
- Coagulation:International normalized ratio.

Actual values and changes from baseline in clinical chemistry, hematology and coagulation, will be summarized by treatment.

Shift tables for clinical chemistry, hematology, and coagulation from baseline CTCAE toxicity for each visit and to the maximum grade on treatment for each parameter will be provided. Participants with both a non-missing baseline and at least one non-missing post-baseline grade will be included in the shift tables. Unscheduled data will be included in the worst case across all scheduled and unscheduled visits after the first dose of study treatment. This means that if there are CTCAE grades derived from both unscheduled and scheduled visits data per test per participant then the highest grade will be summarized.

For non-CTCAE gradable tests, a shift table will be provided showing shifts relative to the normal ranges. This summary of normal range category changes illustrates the number and percentage of participants who fall into specified categories (Decrease to Low, Change to Normal or No Change, Increase to High) by comparing the baseline normal range category to the overall worst-case normal range category. The worst-case post-baseline row will be used to summarize the participants' overall worst-case normal range category change. The determination of the worst-case takes into account both planned and unscheduled assessments. Only laboratory tests which cannot be graded per CTCAE v. 5.0 specified criteria will be included.

Participants with missing baseline value are to be assumed to have normal baseline value. Worst-case can be either High or Low. If a participant has a Decrease to Low and an Increase to High during the same time interval, then the participant is counted in both the 'Decrease to Low' and 'Increase to High' categories. If a participant was high at baseline and decreases to Low during the time interval, then the participant is counted in the 'Decrease to Low' category. Likewise, if a participant was Low at baseline and increases to High during the time interval, then the participant is counted in the 'Increase to High' category. Participants are only counted in the 'Change to Normal or No Change' category if they are:

 Normal at baseline and have no normal range High and no normal range Low values during the time interval

- High at baseline and do not change to Low during the time interval
- Low at baseline and do not change to High during the time interval

Shift tables by treatment will be produced for these laboratory parameters. These tables will summarize the number of participants with each baseline grade relative to the reference ranges and changes to the worst highest grade assessed post-dose during the study.

All events of ALT \geq 3 × upper limit of normal (ULN) and bilirubin \geq 2 ×ULN (> 35% direct bilirubin) or ALT \geq 3 × ULN and international normalized ratio (INR) > 1.5, if INR measured which may indicate severe liver injury (possible Hy's Law), must be reported as an SAE. Liver function results will be presented in a summary table and eDISH (evaluation of drug-induced serious hepatotoxicity) plots.

All laboratory results, as well as CTCAE grades will be included in data listings. Abnormal results for clinical chemistry, hematology, urinalysis and coagulation will be listed separately. Laboratory results for serology, pregnancy tests, FSH, urine drug screen, alcohol breath test, IRR lab data and signs of infection lab data will be listed only.

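### High glucose and high hemoglobin fall into neither laboratory shift table, because SAP 12.2 grades both tests low only yet treats them as fully graded

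*SAP*

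**What the plan says.** SAP 12.2 (Laboratory Evaluations) introduces a list with "The following parameters are CTCAE gradable" and names 15 tests. Two entries carry a limit on direction: "glucose (only do the grading the hypoglycemia, no grading for hyperglycemia" and "hemoglobin (only do the grading for anemia, no grading for hemoglobin increased". No other entry on the list has such a note.

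Two kinds of shift table follow.

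- **Grade shift tables**, for chemistry, hematology and coagulation. They run "from baseline CTCAE toxicity for each visit and to the maximum grade on treatment for each parameter will be provided". They take participants who have a grade at baseline and at least one grade afterwards, and the worst grade takes in unscheduled results.
- **Normal-range shift table.** Its scope is set by "For non-CTCAE gradable tests, a shift table will be provided showing shifts relative to the normal ranges". It counts participants who moved to low, moved to high, or did neither, again with unscheduled results in the worst case. The scope is then repeated as a restriction: "Only laboratory tests which cannot be graded per CTCAE v. 5.0 specified criteria will be included".

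SAP 7.4 (Visit Windows) keeps unscheduled assessments out of summaries, apart from their possible use as the baseline value. SAP 12.2 also plans summaries of actual values and changes from baseline, full laboratory listings, and a separate listing of abnormal results. Clinical laboratory results are part of the primary safety endpoint (SAP 5.1; Protocol Section 3).

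**The concern.** The two shift tables are written as complements: a test goes to one or the other, and between them they should show every shift. That works only if a gradable test is graded in every direction that matters. For glucose and hemoglobin the SAP switches off one direction and still treats the test as gradable. The restriction on the normal-range table then shuts out the direction that was switched off.

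At stake is a count in a primary-endpoint output. The study tests no hypotheses (Protocol 9.1), so its safety comparison rests on descriptive tables. For a non-gradable test, the reader can see how many participants on each treatment went above the normal range at any time, including at unscheduled draws. For glucose and hemoglobin no shift table gives that count.

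**Working it through.** The plan states no figure on this point to reproduce. The check is a count of the tests, followed by a trace of each test and direction through the two inclusion rules.

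**Count of tests (SAP 12.2)**

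- Graded: 9 chemistry + 5 hematology + 1 coagulation = 15.
- Named in the parameter lists: 22 chemistry + 12 hematology + 3 coagulation = 37, counting total and direct bilirubin separately.
- Of the 15 graded tests, 14 are among those 37. Total leukocytes is graded but is missing from the SAP's hematology parameter list.
- Tests eligible for the normal-range table: 37 − 14 = 23. Glucose and hemoglobin are not among them.

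**Trace by direction**

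| Test and direction | Graded in SAP 12.2? | Can shift in the grade table? | Admitted to the normal-range table? |
|---|---|---|---|
| Glucose, low | Yes | Yes | No, test is gradable |
| Glucose, high | No | No | No, test is gradable |
| Hemoglobin, low | Yes | Yes | No, test is gradable |
| Hemoglobin, high | No | No | No, test is gradable |

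Two of the four pairs are covered by a shift table. With the exclusion applied by direction, the two high pairs enter the normal-range table. Coverage becomes four of four, and low values are not counted twice.

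**Does another sentence close the gap?** SAP 12.2 ends this part with a general statement about shift tables by treatment, which speaks of baseline grade in relation to the reference ranges. It closely follows Protocol 9.4.1. It comes after the normal-range rules and does not lift their restriction. At most it makes the text ambiguous.

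**Where a high value can still be seen**

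| Output | Scheduled high value | Unscheduled high value |
|---|---|---|
| Summary of actual values and changes (SAP 7.1, 12.2) | Yes, through the mean and maximum; no count above range | No (SAP 7.4) |
| Either shift table | No | No |
| Laboratory and abnormal-results listings (SAP 12.2) | Yes | Yes |
| Treatment-emergent adverse event tables (SAP 12.1) | If recorded as an adverse event | If recorded as an adverse event |

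An unscheduled high value therefore reaches a summary table only if it is recorded as an adverse event.

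**The case against.** The strongest reply is that little is lost. Protocol 8.2.4 has the investigator record clinically relevant laboratory changes as adverse events. Protocol 10.3.1 lists abnormal laboratory results among events that meet the adverse event definition. SAP 12.1 tabulates those events with participant counts. The maximum of scheduled values is shown and every abnormal result is listed. With six active participants planned per cohort, and only two participants in all in Cohort 2, a reviewer will read the data participant by participant. High glucose and high hemoglobin are also not among the risks named in Protocol Table 13.

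Most of this stands, and it limits the size of the point. It does not remove it. Adverse event recording depends on the investigator's judgment, whereas a shift table applies the same rule to every result. The SAP gives the 23 non-gradable tests that treatment and gives no reason to withhold it from these two in the high direction.

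A reader might infer more than the documents support:

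- **That neutrophils, leukocytes and platelets have the same gap, so a sign of infection would be missed.** The SAP states a direction limit for glucose and hemoglobin only. The numeric CTCAE criteria for the other tests are not in the documents, so this cannot be settled from them.
- **That the SAP departs from the protocol without saying so.** Protocol 9.4.1 mixes grades and reference ranges and promises no separate high/low table for graded tests. That table is the SAP's addition.
- **That these participants will be displayed as having no toxicity.** The SAP does not say how a value in an ungraded direction is displayed.
- **That the incidence of high values would be zero in every table.** The gap is in the shift tables; the adverse event tables can still count such values.

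**Conclusion.** The point holds for glucose and hemoglobin. Followed as written, SAP 12.2 leaves shifts to high values of these two tests out of both laboratory shift tables, and SAP 7.4 keeps unscheduled high values out of the descriptive summaries as well. This is a stated rule with an unintended hole, not a detail left for later.

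The size is 2 of 15 graded tests, one direction each. The effect is on tabulation only: no data are lost, and nothing here shows that a safety conclusion would change. It is a modest gap in a primary-endpoint output, worth correcting because the correction is so small.

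The verdict rests on two readings: that the restriction on the normal-range table applies to the whole test, and that the general closing statement on shift tables does not override it. If the sponsor intended otherwise, the wording still needs to say so.

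**What to change.** In SAP 12.2, replace the sentence that limits the normal-range shift table to non-gradable tests with a rule by test and direction. Suggested content: the table includes every test without a CTCAE grade and, for graded tests, any direction that this SAP does not grade; this covers high glucose and high hemoglobin, and any other listed test whose numeric grading the sponsor confirms to be in one direction only. The existing worst-case rule, which includes unscheduled results, applies.

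Two details should go in the table footnote:

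- For these tests the low direction is reported by grade in the other table, so the reader does not take the remaining category to mean no low values.
- The two tables treat a missing baseline differently. The normal-range table assumes it to be normal, while the grade table leaves the participant out. Denominators can therefore differ.

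The sponsor should also check the other 13 graded tests once against the CTCAE version in use and record which directions are graded.

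The cost is one SAP sentence, a footnote and a few rows in a table already planned. No new data are needed. The downside is a slightly longer table.
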